Appendix 1 Schedule of Assessments (cont.)

Arm C: Regorafenib Schedule of Assessments

	Screening ^a	Cycle 1				Cycle 2			Cycle 3 +	Treatment Discontinuation ^b	Survival FU ^c
Day	-35 to 1	1	8	15	22	1	8	15	1	< 30 d after last dose	q3m
Informed consent ^d	x										
Demographics	x										
Medical and CRC history	x										
Vital signs ^{e,f}	x	x	x	x	x	x	x	x	x		
ECOG PS	x	x				x			x		
Weight	x	x				x			x		
Height	x										
Complete physical examination	x										
Limited physical examination		x ^g				x			x		
Hematology ^h	x	x				x			x		
Coagulation (INR and aPTT)	x										
Chemistry ^j	x	x		x		x		x	x		
CEA		x				x			x	x	
WGS (Optional)		x									
ECHO/MUGA	x										
Tumor assessments	x	Scan assessments every 8 weeks ^j									
Serology ^k	x										
Thyroid function	x										

Appendix 1 Schedule of Assessments (cont.)

Ophthalmologic exam	x										
Pregnancy test ^l	x	x				x			x		
Adverse events	x ^m	x	x	x	x	x	x	x	x	x ⁿ	x

Arm C: Regorafenib Schedule of Assessments (cont.)

	Screening ^a	Cycle 1				Cycle 2			Cycle 3 +	Treatment Discontinuation ^b	Survival FU ^c
Day	-35 to 1	1	8	15	22	1	8	15	1	< 30 d after last dose	q3m
Tumor biopsy ^o	x			x						x	
Concomitant medications	x	x				x			x	x	
EORTC QLQ-C30, EQ-5D-5L ^p		x				x			x	x	x
Survival and anti-cancer therapy follow-up											x ^q
Biomarker blood samples		x				x			x	x	
Regorafenib administration ^f		x				x			x		

ATA = anti-therapeutic antibody; C3 = Cycle 3; C4 = Cycle 4; CEA = carcinoembryonic antigen; CRC = colorectal cancer; d = day; ECHO = echocardiogram; ECOG PS = Eastern Cooperative Oncology Group Performance Status; EORTC QLQ-C30 = European Organization for Research and Treatment of Cancer Quality of Life-C30 questionnaire; EQ-5D-5L = EuroQoL 5 Dimensions; FU = follow-up; MUGA = multigated acquisition scan; PK = pharmacokinetic; q3m = every 3 months; WGS = whole genome sequencing.

^a Results of standard of care tests or examinations performed prior to obtaining informed consent and within 35 days prior to Day 1 may be used; such tests do not need to be repeated for screening.

^b Patients who discontinue study drug will return to the clinic for a treatment discontinuation visit

^c Required follow-up information will be collected via telephone calls and/or clinic visits every 3 months until death, withdrawal of consent, the patient is lost to follow-up, or study termination by the Sponsor, whichever occurs first. .

Appendix 1 Schedule of Assessments (cont.)

- ^d Informed consent must be documented before and study-specific screening procedure is performed and may be obtained up to 35 days before initiation of study treatment
- ^e Includes respiratory rate, heart rate, temperature, and systolic and diastolic blood pressure while the patient is in a seated position. Record abnormalities observed at baseline on the General Medical History and Baseline Conditions eCRF. At subsequent visits record new or worsened clinically significant abnormalities on the Adverse Event eCRF
- ^f Monitor vital signs weekly for the first 6 weeks and then with every cycle, especially systolic and diastolic blood pressure.
- ^g If physical examinations are assessed within 7 days of the Cycle 1 Day 1 visit, they do not have to be repeated at Day 1.
- ^h Hematology (CBC, hemoglobin, hematocrit, WBC count with differential [neutrophils, eosinophils, lymphocytes, monocytes, basophils, and other cells], and platelet count)
- ⁱ Serum chemistry (glucose, BUN or urea, creatinine, sodium, potassium, magnesium, calcium, phosphorus, total bilirubin, ALT, AST, ALP, LDH, CPK, lipase, amylase, [albumin and LDH at screening only]). LFTs are tested every 2 weeks for the first 2 months of treatment and then at every cycle thereafter. All other labs are tested at the beginning of each cycle.
- ^j Tumor assessments will continue until disease progression per RECIST v1.1, loss of clinical benefit (patients who continue treatment after disease progression according to RECIST v1.1), consent withdrawal, study termination by the Sponsor, or death, whichever occurs first. Patients who discontinue treatment for reasons other than disease progression (e.g., toxicity) will continue scheduled tumor assessments until disease progression, withdrawal of consent, study termination by Sponsor, or death, whichever occurs first.
- ^k All patients will be tested for HIV prior to the inclusion into the study and HIV-positive patients will be excluded from the clinical study. HBV serology will include HBsAg, antibodies against HBsAg, total HBcAg antibody (anti-HBcAb). HBV DNA should be obtained prior to randomization if patient has a negative serology for HBsAg and a positive serology for anti-HBcAb. HCV serology will include HCV antibody (anti-HCV). HCV RNA should be obtained prior to randomization if patient tests positive for anti-HCV
- ^l All women of childbearing potential will have a serum pregnancy test within 14 days before Cycle 1 Day 1. Urine pregnancy tests will be performed at specific subsequent visits. If a urine pregnancy test is positive, it must be confirmed by a serum pregnancy test. Refer to Section 5.4.3 for details.
- ^m Only serious adverse events caused by protocol-mandated intervention should be reported
- ⁿ All serious adverse events and Adverse Events of Special Interest, regardless of relationship to study drug, will be reported until 90 days after the last dose of study drug or initiation of new anti-cancer therapy, whichever occurs first. All other adverse events, regardless of relationship to study drug, will be reported until 30 days after the last dose of study drug or initiation of new anti-cancer therapy, whichever occurs first. After this period the investigator should report any serious adverse events or adverse events of special interest that are believed to be related to prior study drug.

Appendix 1 Schedule of Assessments (cont.)

- ° Archival or fresh baseline tumor tissue collected during screening; Optional on treatment biopsy at Cycle 1 Day 15±5 days; Mandatory biopsy at progression.
- ° PRO instruments EORTC QLQ-C30 and EQ-5D-5L will be completed in this order using an electronic device on Day 1 of each cycle during a visit and prior to any assessments. Data will be collected at end of study treatment and at survival follow-up at 3 and 6 months only. In the event a study visit is conducted by telephone, the PRO data for that visit will be collected via telephone interview and recorded by the investigative staff on the ePRO tablet. To maintain validity and minimize patient burden, the PRO instruments administered via telephone interview will consist of a subset of the EORTC QLQ items (Items 1-7, 10, 12, 13, 16, 17, 18, 29 and 30 from the C30 and the two additional items from the item bank) and the telephone interview version of the EQ-5D-5L.
- ° Patients who discontinue treatment for reasons other than disease progression (e.g., toxicity) will continue scheduled tumor assessments until disease progression, withdrawal of consent, study termination by Sponsor, or death, whichever occurs first.
- ° Regorafenib 160 mg/day PO will be given in a 21/7 dosing schedule. Dose can be given ±7 days from Day 1 but the scheduled 7-day break must be ≥5 days.

Appendix 2

Schedule of Pharmacokinetic and Immunogenicity Samples

Visit	Timepoint	Sample Type	Drug
^a Cycle 1 Day 15 ^a Cycle 4 Day 15	Predose and 3 to 6 hours after dose	Plasma PK	Cobimetinib
Day 1 of Cycles 1–4	Predose (prior to infusion)	Serum PK	Atezolizumab
		Serum ATA	Atezolizumab
Day 1 of Cycles 1 and 4	30 minutes (\pm 10) after infusion	Serum PK	Atezolizumab
Day 1 of Cycle 8 and every 8 cycles after Cycle 8	Predose (prior to infusion)	Serum PK	Atezolizumab
		Serum ATA	Atezolizumab
Treatment discontinuation ^b	At visit	Serum PK	Atezolizumab
		Serum ATA	Atezolizumab
120 days \pm 30 days after treatment discontinuation ^b	At visit	Serum PK	Atezolizumab
		Serum ATA	Atezolizumab

ATA=anti-therapeutic antibody; PK=pharmacokinetic.

^a Arm A (cobimetinib with atezolizumab) only.

^b These samples will be collected provided that the blood draws are clinically feasible and do not cause the patient undue hardship (e.g., the patient is in hospice care and not able to come in for a visit).

Appendix 3

Management of Cobimetinib plus Atezolizumab–Associated Adverse Events (Arm A)

Note: For information regarding management of atezolizumab-associated adverse events, including infusion-related reactions and immune-related events (e.g., endocrine, ocular, pancreatic, and neurologic events), please refer [Appendix 9](#).

GASTROINTESTINAL TOXICITY

Diarrhea and colitis have been associated with the administration of cobimetinib plus atezolizumab.

Diarrhea can frequently be managed with anti-diarrheal agents but can also progress to clinically significant dehydration and/or electrolyte imbalances with effects on other organs, possibly resulting in renal, hepatic, and/or cardiac failure. Patients should be instructed to promptly contact the investigators if they develop diarrhea. Investigators should treat diarrhea and intervene promptly for patients who appear to be at increased risk of developing significant dehydration, electrolyte imbalances, and/or multi-organ failure. Patients should receive maximum supportive care per institutional guidelines.

See [Table 1](#) for guidelines on how to manage gastrointestinal toxicity in patients treated with cobimetinib plus atezolizumab.

Appendix 3 Management of Cobimetinib plus Atezolizumab–Associated Adverse Events (Arm A) (cont.)

Table 1 Guidelines for Managing Atezolizumab- and Cobimetinib-Associated Gastrointestinal Toxicity

Event	Action to be Taken
Gastrointestinal events: general guidance	
All events of diarrhea or colitis should be thoroughly evaluated for more common etiologies other than drug induced effects.
 
For events of significant duration or severity or associated with signs of systemic inflammation or acute phase reactants, check for immune-related colitis.
 
Administer anti-diarrheal agents and other maximal supportive care per institutional guidelines such as: at the first report of watery diarrhea or loose stool, initiate maximal anti-diarrheal supportive care (Lomotil and loperamide).
 
Suggested regimen:
 
 ○ Loperamide: Initiate dose with 4 mg, then 4 mg/6 hr around the clock, alternating with Lomotil. ○ Lomotil (diphenoxylate and atropine): 2 tablets (diphenoxylate 5 mg, atropine 0.05 mg) every 6 hr around the clock ○ Continue Lomotil and loperamide until no loose stools for 24 hours. ○ If Grade \leq 2 diarrhea persists after 48 hr total treatment with Lomotil and loperamide, consider second-line agents (e.g., octreotide, budesonide, tincture of opium). 
Oral supplementation:
 
 ○ Initiate oral supplementation of potassium and/or magnesium if serum levels are <LLN. ○ Consider oral rehydration therapy (e.g., Pedialyte[®]) for Grade \geq 1 diarrhea or vomiting. 
Dietary modifications:
 
 ○ Stop all lactose-containing products and eat small meals. ○ The BRAT (banana, rice, apples, toast) diet, without fiber (other vegetables and fruits), may be helpful. ○ Encourage adequate hydration with salt-containing liquids, such as broth or Gatorade.
Diarrhea, Grade 1 or Grade 2 (tolerable)	
Continue atezolizumab and cobimetinib.
 
Initiate supportive care and monitor patient closely
 
Investigate etiology, referring patient to GI specialist for evaluation of possible colitis if appropriate.

Appendix 3 Management of Cobimetinib plus Atezolizumab–Associated Adverse Events (Arm A) (cont.)

Table 1 Guidelines for Managing Atezolizumab- and Cobimetinib-Associated Gastrointestinal Toxicity (cont.)

Event	Management
Diarrhea, Grade 2 (intolerable) or Grade 3	
Withhold atezolizumab and cobimetinib. Initiate supportive care and monitor patient closely. Discontinue medications that may exacerbate colitis (e.g., NSAIDS) while investigating etiology. Investigate etiology, referring patient to GI specialist for evaluation of possible colitis, including biopsy if appropriate. If event resolves to Grade 1 or better within 12 weeks, resume atezolizumab at fixed dose. If not, permanently discontinue atezolizumab and cobimetinib. ^{a,b,c} If event resolves to Grade 1 or better within 28 days, resume cobimetinib with dose reduced by one level. If not, permanently discontinue cobimetinib.

Diarrhea, Grade 4	
Permanently discontinue atezolizumab and cobimetinib, and contact Medical Monitor. ^c Initiate supportive care and monitor patient closely. Discontinue medications that may exacerbate colitis (e.g., NSAIDS) while investigating etiology. Rule out bowel perforation. Investigate etiology, referring patient to GI specialist for evaluation of possible colitis, including biopsy if appropriate.

Colitis, Grade 1	
Continue atezolizumab and cobimetinib. Initiate supportive care and monitor patient closely. Discontinue medications that may exacerbate colitis (e.g., NSAIDS). Refer patient to gastrointestinal specialist for evaluation and confirmatory biopsy if symptoms persist for > 7 days.

Colitis, Grade 2	
Withhold atezolizumab and cobimetinib. Initiate supportive care and monitor patient closely. Discontinue medications that may exacerbate colitis (e.g., NSAIDS). Refer patient to gastrointestinal specialist for evaluation and confirmatory biopsy. For recurrent events or events that persist >5 days, initiate treatment with 1–2 mg/kg/day oral prednisone or equivalent. If event resolves to Grade 1 or better within 12 weeks, resume atezolizumab at fixed dose. If not, permanently discontinue atezolizumab and cobimetinib. ^{a,b,c} If event resolves to Grade 1 or better within 28 days, resume cobimetinib with dose reduced by one level. If not, permanently discontinue cobimetinib.

Appendix 3 Management of Cobimetinib plus Atezolizumab–Associated Adverse Events (Arm A) (cont.)

Table 1 Guidelines for Managing Atezolizumab- and Cobimetinib-Associated Gastrointestinal Toxicity (cont.)

Colitis, Grade 3	
Withhold atezolizumab and cobimetinib. Initiate supportive care and monitor patient closely. Discontinue medications that may exacerbate colitis (e.g., NSAIDs). Refer patient to gastrointestinal specialist for evaluation and confirmatory biopsy. Initiate treatment with 1–2 mg/kg/day IV methylprednisolone or equivalent and convert to 1–2 mg/kg/day oral prednisone or equivalent upon improvement. If event resolves to Grade 1 or better within 12 weeks, resume atezolizumab at fixed dose. If not, permanently discontinue atezolizumab and cobimetinib.^{a,b,c} If event resolves to Grade 1 or better within 28 days, resume cobimetinib with dose reduced by one level. If not, permanently discontinue cobimetinib.

Colitis, Grade 4	
Permanently discontinue atezolizumab and cobimetinib, and contact Medical Monitor.^c Initiate supportive care and monitor patient closely. Discontinue medications that may exacerbate colitis (e.g., NSAIDs). Refer patient to gastrointestinal specialist for evaluation and confirmatory biopsy. Initiate treatment with 1–2 mg/kg/day IV methylprednisolone or equivalent and convert to 1–2 mg/kg/day oral prednisone or equivalent upon improvement. If event does not improve within 48 hours after initiating corticosteroids, consider adding an immunosuppressive agent. If event resolves to Grade 1 or better, taper corticosteroids over ≥ 1 month.

GI = gastrointestinal; IV = intravenous; NSAID = non-steroidal anti-inflammatory drug.

^a If corticosteroids have been initiated, they must be tapered over ≥ 1 month to ≤ 10 mg/day oral prednisone or equivalent before atezolizumab can be resumed.

^b Atezolizumab may be withheld for a period of time beyond 12 weeks to allow for corticosteroids to be reduced to ≤ 10 mg/day oral prednisone or equivalent. The acceptable length of the extended period of time must be agreed upon by the investigator and the Medical Monitor.

^c Resumption of atezolizumab may be considered in patients who are deriving benefit and have fully recovered from the immune-related event. Patients can be rechallenged with atezolizumab only after approval has been documented by both the investigator (or an appropriate delegate) and the Medical Monitor.

Appendix 3 Management of Cobimetinib plus Atezolizumab–Associated Adverse Events (Arm A) (cont.)

HEPATOTOXICITY

Hepatotoxicity has been associated with the administration of atezolizumab and cobimetinib. Eligible patients must have adequate liver function, as manifested by measurements of total bilirubin and hepatic transaminase, and liver function will be monitored throughout study treatment.

While in this study, patients presenting with right upper-quadrant abdominal pain and/or unexplained nausea or vomiting should have liver function tests (LFTs) performed immediately and reviewed before administration of the next dose of study drug.

If LFTs increase, neoplastic, concurrent medications, viral hepatitis, and toxic etiologies should be considered and addressed, as appropriate. Imaging of the liver, gall bladder, and biliary tree should be performed to rule out neoplastic or other causes for the increased LFTs. Anti-nuclear antibody, perinuclear anti-neutrophil cytoplasmic antibody, anti-liver kidney microsomal antibodies, and anti-smooth muscle antibody tests should be considered.

Patients with LFT abnormalities should be managed according to the guidelines in [Table 2](#).

Appendix 3 Management of Cobimetinib plus Atezolizumab–Associated Adverse Events (Arm A) (cont.)

Table 2 Guidelines for Managing Atezolizumab and Cobimetinib–Associated Hepatotoxicity

LFT Abnormalities	Management
AST/ALT > ULN to $\leq 3 \times$ ULN with total bilirubin < $2 \times$ ULN	Continue atezolizumab and cobimetinib. Continue with the standard monitoring plan (i.e., LFTs q4w before dosing).
AST/ALT > $3 \times$ baseline values to < $5 \times$ ULN with total bilirubin < $2 \times$ ULN	Continue all study treatment. Monitor LFTs at least weekly. Consider referral to a hepatologist and liver biopsy. For suspected immune related events of > 5 days duration 
 ○ Consider withholding atezolizumab ^c ○ Consider administering 1-2 mg/kg/day oral prednisone or equivalent followed by ≥ 1 month taper ○ Restart atezolizumab if event resolves to Grade 1 or better within 12 weeks ^{a, b} ○ Permanently discontinue atezolizumab and cobimetinib if event does not resolve to Grade 1 or better within 12 weeks ^{a, b, c}
AST/ALT > $5 \times$ baseline values to < $10 \times$ ULN with total bilirubin < $2 \times$ ULN	Continue all study treatment. Monitor LFTs at least weekly. Consider referral to a hepatologist and liver biopsy. For suspected immune related events 
 ○ Withhold atezolizumab ○ Consider administering 1-2 mg/kg/day oral prednisone or equivalent followed by ≥ 1 month taper ○ If event does not improve within 48 hours after initiating corticosteroids, consider adding an immunosuppressive agent. If event resolves to Grade 1 or better, taper corticosteroids over ≥ 1 month. ○ Permanently discontinue atezolizumab and cobimetinib if event does not resolve to Grade 1 or better within 12 weeks ^{a, b, c}

Appendix 3 Management of Cobimetinib plus Atezolizumab–Associated Adverse Events (Arm A) (cont.)

Table 2 Guidelines for Managing Atezolizumab and Cobimetinib–Associated Hepatotoxicity (cont.)

LFT Abnormalities	Management
AST/ALT > 3 × ULN with bilirubin > 2 × ULN	
Withhold atezolizumab and cobimetinib. Consult hepatologist and consider liver biopsy. Consider administering 1-2 mg/kg/day oral prednisone or equivalent followed by ≥ 1 month taper (for possible autoimmune hepatitis). If LFTs do not decrease within 48 hours after initiation of systemic steroids, consider adding an immunosuppressive agent (e.g., mycophenolate or TNF-α antagonist). Monitor LFTs every 48–72 hr until decreasing and then follow weekly. Restart atezolizumab at fixed dose and cobimetinib at 1 dose reduction after discussion with medical monitor if AST/ALT < 3 × ULN with bilirubin < 2 × ULN and steroid dose < 10 mg oral prednisone equivalent per day.^{a, b, c} Permanently discontinue atezolizumab and cobimetinib for life-threatening hepatic events, and contact the Medical Monitor.

AST/ALT > 10 × ULN	
Permanently discontinue atezolizumab and cobimetinib.^c Consult hepatologist and consider liver biopsy. Consider administering 1–2 mg/kg/day oral prednisone or equivalent (for possible autoimmune hepatitis). If event resolves to Grade 1 or better, taper corticosteroids over ≥ 1 month. If LFTs do not decrease within 48 hr after initiation of systemic steroids, addition of an alternative immunosuppressive agent (e.g., mycophenolate or TNF-α antagonist) or dose escalation of corticosteroids may be considered. Monitor LFTs every 48–72 hours until decreasing and then follow weekly.

IV = intravenous; LFT = liver function test; q4w = every 4 weeks; TNF = tumor necrosis factor; ULN = upper limit of normal.

- ^a If corticosteroids have been initiated, they must be tapered over ≥ 1 month to ≤ 10 mg/day oral prednisone or equivalent before atezolizumab can be resumed.
- ^b Atezolizumab may be withheld for a period of time beyond 12 weeks to allow for corticosteroids to be reduced to ≤ 10 mg/day oral prednisone or equivalent. The acceptable length of the extended period of time must be agreed upon by the investigator and the Medical Monitor.
- ^c Resumption of atezolizumab may be considered in patients who are deriving benefit and have fully recovered from the immune-related event. Patients can be re-challenged with atezolizumab only after approval has been documented by both the investigator (or an appropriate delegate) and the Medical Monitor.

**Appendix 3 Management of Cobimetinib plus Atezolizumab–Associated
Adverse Events (Arm A) (cont.)**

DERMATOLOGIC TOXICITY

Treatment-emergent rash has been associated with atezolizumab and cobimetinib. The majority of the cases of rash were mild in severity and self-limited, with or without pruritus.

A dermatologist should evaluate persistent and/or severe rash or pruritus. A biopsy should be considered unless contraindicated.

Dermatologic toxicity and rash should be managed according to the guidelines in [Table 3](#).

Appendix 3 Management of Cobimetinib plus Atezolizumab–Associated Adverse Events (Arm A) (cont.)

Table 3 Guidelines for Managing Atezolizumab and Cobimetinib Rash

Dermatologic Toxicity/Rash (e.g., maculo-papular or purpura)	Management
Dermatologic event, Grade 1/2	
Continue atezolizumab and cobimetinib.
 
Initiate supportive care (e.g., antihistamines, topical corticosteroids).
 
For Grade 2 rash, consider referral to dermatologist.
 
Acneiform rash:
 
Consider topical corticosteroids (hydrocortisone 2.5%, alclometasone) and oral antibiotics (minocycline, doxycycline, or antibiotics covering skin flora) BID for at least 4 weeks.

Dermatologic event, Grade 3	
Withhold atezolizumab and cobimetinib.
 
Refer patient to dermatologist. A biopsy should be performed if appropriate, and, if possible, photographs of the rash should be obtained and submitted to the Sponsor.
 
Consider initiating treatment with 10 mg/day oral prednisone or equivalent, increasing dose to 1–2 mg/kg/day if event does not improve within 48–72 hours.
 
If event resolves to Grade 2 or better within 12 weeks, resume atezolizumab at fixed dose. If not, permanently discontinue atezolizumab.^{a,b}
 
Permanently discontinue atezolizumab and contact Medical Monitor if event does not resolve to Grade 1 or better within 12 weeks.^{a, b, c}
 
If event resolves to Grade 2 or better within 28 days, resume cobimetinib with dose reduced by one level. If not, permanently discontinue cobimetinib.
 
Acneiform rash:
 
Consider continuation of topical corticosteroids 2.5%, alclometasone) and oral antibiotics (minocycline, doxycycline or antibiotics covering skin flora) when restarting cobimetinib.

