Appendix 3 Management of Cobimetinib plus Atezolizumab–Associated Adverse Events (Arm A) (cont.)

Table 3 Guidelines for Managing Atezolizumab and Cobimetinib Rash (cont.)

Dermatologic Toxicity/Rash (e.g., maculo-papular or purpura)	Management
Dermatologic event, Grade 4	Permanently discontinue all study treatment and contact Medical Monitor.

BID = twice daily; BSA = body surface area; PRN = as needed.

- ^a If corticosteroids have been initiated, they must be tapered over ≥ 1 month to ≤ 10 mg/day oral prednisone or equivalent before atezolizumab can be resumed.
- ^b Atezolizumab may be withheld for a period of time beyond 12 weeks to allow for corticosteroids to be reduced to ≤ 10 mg/day oral prednisone or equivalent. The acceptable length of the extended period of time must be agreed upon by the investigator and the Medical Monitor.
- ^c Resumption of atezolizumab may be considered in patients who are deriving benefit and have fully recovered from the immune-related event. Patients can be rechallenged with atezolizumab only after approval has been documented by both the investigator (or an appropriate delegate) and the Medical Monitor.

PULMONARY TOXICITY

Mild-to-moderate events of pneumonitis have been reported with atezolizumab and cobimetinib. All pulmonary events should be thoroughly evaluated for other commonly reported etiologies such as pneumonia/infection, lymphangitic carcinomatosis, pulmonary embolism, heart failure, chronic obstructive pulmonary disease, or pulmonary hypertension.

Pulmonary toxicity should be managed per the guidelines in [Table 4](#).

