Table 9 Management Guidelines for Dermatologic Events

Event	Management
Dermatologic event, Grade 1	
 • Continue atezolizumab. • Consider treatment with topical corticosteroids and/or other symptomatic therapy (e.g., antihistamines).
Dermatologic event, Grade 2	
 • Continue atezolizumab. • Consider patient referral to dermatologist. • Initiate treatment with topical corticosteroids. • Consider treatment with higher-potency topical corticosteroids if event does not improve.
Dermatologic event, Grade 3	
 • Withhold atezolizumab for up to 12 weeks after event onset. ^a • Refer patient to dermatologist. • Initiate treatment with 10 mg/day oral prednisone or equivalent, increasing dose to 1–2 mg/kg/day if event does not improve within 48–72 hours. • If event resolves to Grade 1 or better, resume atezolizumab. ^b • If event does not resolve to Grade 1 or better while withholding atezolizumab, permanently discontinue atezolizumab and contact Medical Monitor. ^c
Dermatologic event, Grade 4	
 • Permanently discontinue atezolizumab and contact Medical Monitor. ^c

^a Atezolizumab may be withheld for a longer period of time (i.e., >12 weeks after event onset) to allow for corticosteroids (if initiated) to be reduced to ≤10 mg/day oral prednisone or equivalent. The acceptable length of the extended period of time must be agreed upon by the investigator and the Medical Monitor.

^b If corticosteroids have been initiated, they must be tapered over ≥1 month to ≤10 mg/day oral prednisone or equivalent before atezolizumab can be resumed.

^c Resumption of atezolizumab may be considered in patients who are deriving benefit and have fully recovered from the immune-related event. Patients can be re-challenged with atezolizumab only after approval has been documented by both the investigator (or an appropriate delegate) and the Medical Monitor.

Appendix 9: Risks Associated with Atezolizumab and Guidelines for Management of Adverse Events Associated with Atezolizumab (cont.)

NEUROLOGIC DISORDERS

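### Two Arm A toxicity rules in Protocol Appendix 3 cannot be applied as written: the Grade 3 rash cell gives atezolizumab two different week-12 thresholds, and the transaminase table has no row for many rises from a raised baseline

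*Protocol*

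**What the plan says.** **Rash (Protocol Appendix 3, Table 3, Grade 3 row).** Both drugs are withheld. The cell then gives two atezolizumab rules with the same 12-week limit. The first is "If event resolves to Grade 2 or better within 12 weeks, resume atezolizumab at fixed dose", followed by permanent discontinuation if that is not met. The second is "Permanently discontinue atezolizumab and contact Medical Monitor if event does not resolve to Grade 1 or better within 12 weeks". The cobimetinib line uses the Grade 2 threshold: "If event resolves to Grade 2 or better within 28 days, resume cobimetinib with dose reduced by one level". Footnote a concerns the steroid taper and footnote b a longer hold to allow that taper. Footnote c concerns rechallenge: "Resumption of atezolizumab may be considered in patients who are deriving benefit and have fully recovered from the immune-related event". The corresponding Grade 3 rule in Appendix 9, Table 9 is "If event resolves to Grade 1 or better, resume atezolizumab".

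**Liver (Protocol Appendix 3, Table 2).** With bilirubin below 2×ULN:

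- Row 1 covers values above ULN up to and including 3×ULN.
- Row 2 is "AST/ALT > $3 \times$ baseline values to < $5 \times$ ULN".
- Row 3 is "AST/ALT > $5 \times$ baseline values to < $10 \times$ ULN".

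A further row needs bilirubin above 2×ULN, and the last row stops both drugs above 10×ULN. Rows 2 and 3 both begin by keeping study treatment going, with liver tests at least weekly. They prompt hepatologist referral, biopsy and prednisone. An atezolizumab hold applies only to suspected immune-related events: row 2 says to consider it ("For suspected immune related events of > 5 days duration"), and row 3 says to do it.

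**Eligibility (Protocol 4.1.1).** AST and ALT may be up to 2.5×ULN at entry, or 5×ULN with documented liver metastases.

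**The concern.** These tables tell sites how to manage two expected toxicities in the largest arm (about 180 patients), and both study drugs are associated with rash and liver toxicity.

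For a rash at Grade 2 at week 12, whichever action the site takes departs from one line of the cell, and Protocol 9.2 does not allow deviations to be agreed in advance.

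For liver tests, a lower limit that moves with the patient's baseline is paired with an upper limit that does not. Once the baseline is high enough, the lower limit passes the upper limit and no value can satisfy the row. Liver metastases are the protocol's own reason for allowing a higher entry limit, so these are patients it means to enrol. A rise from 2 to 9×ULN with normal bilirubin would also meet neither liver trigger for immediate reporting in Protocol 5.2.3 (above 10×ULN, or the Hy's law combination).

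At stake are patient safety and consistent treatment across sites, not the survival analysis.

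**Working it through.** The plan states no figure to reproduce here. The check is a reading of the rash cell and interval arithmetic on the liver rows.

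**Rash: what each line says, by grade at week 12**

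| Grade at week 12 | First line | Second line |
|---|---|---|
| 1 or better | resume | no stop |
| 2 | resume | stop permanently |
| 3 or worse | stop permanently | stop permanently |

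The lines conflict only at Grade 2. The footnotes do not settle it: a and b concern steroid tapering, and c needs full recovery. The surrounding text points both ways. Table 3 continues both drugs for a new Grade 2 rash and restarts cobimetinib at Grade 2, while Appendix 9, Table 9 requires Grade 1.

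**Liver: inputs and intervals.** Let b be baseline and v the current value, both in ×ULN, with bilirubin below 2×ULN.

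- Row 1: 1 < v ≤ 3.
- Row 2: 3b < v < 5. Empty when 3b ≥ 5, that is b ≥ 5/3 (about 1.67).
- Row 3: 5b < v < 10. Empty when 5b ≥ 10, that is b ≥ 2.
- Stop row: v > 10.

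At b = 2, row 2 needs v above 6 and below 5, and row 3 needs v above 10 and below 10. A value of 9×ULN therefore has no row. By the grade bands in the regorafenib table (Protocol 5.1.4.5, Table 6) it is Grade 3.

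Width with no row, among values above baseline from over 3 to 10×ULN:

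| b | Row 2 | Row 3 | No row | Share | Largest rise with no row (10/b) |
|---|---|---|---|---|---|
| 1 | 3–5 | 5–10 | exact values 5 and 10 only | 0% | – |
| 1.25 | 3.75–5 | 6.25–10 | 0.75 + 1.25 = 2.0 of 7 | 29% | – |
| 1.5 | 4.5–5 | 7.5–10 | 1.5 + 2.5 = 4.0 of 7 | 57% | – |
| 1.9 | empty | 9.5–10 | 2.0 + 4.5 = 6.5 of 7 | 93% | – |
| 2 | empty | empty | 7 of 7 | 100% | 5.0-fold |
| 2.5 | empty | empty | 7 of 7 | 100% | 4.0-fold |
| 3 | empty | empty | 7 of 7 | 100% | 3.3-fold |
| 4 | empty | empty | 6 of 6 | 100% | 2.5-fold |
| 5 | empty | empty | 5 of 5 | 100% | 2.0-fold |

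Below b = 1 the rows overlap. At b = 0.5, row 2 starts at 1.5 and row 3 at 2.5, so 1.5 to 5 lies in at least two rows: 3.5 of the 9 units from 1 to 10, or 39%. At b = 0.8 the overlap is 2.4–3 and 4–5: 1.6 of 9, or 18%. The overlapping rows differ in monitoring interval, in the 5-day condition, and in considering a hold versus making one.

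**What could fill the gap**

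- Protocol 5.1.4.1, Table 3: for any Grade 3 or 4 event, interrupt cobimetinib and restart at 40 mg.
- Protocol 5.1.4.2, Table 4: for Grade 3 or 4, interrupt the attributable drug. Abnormalities that are mainly laboratory findings may continue on treatment at the investigator's discretion.
- Appendix 9, Table 2: for a Grade 3 or 4 hepatic event, stop atezolizumab permanently.

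For one laboratory-only Grade 3 rise, atezolizumab could thus be continued under Table 4 or stopped for good under Appendix 9. Protocol 5.1.4.3 and the hepatotoxicity text of Appendix 3 send Arm A to Appendix 3, Table 2, while Protocol 5.1.4.4 sends Arm B to Appendix 9. No sentence says which rule applies to Arm A when Table 2 has no row.

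**The case against.** **The missing rows mostly say to carry on.** This stands. A rise not thought immune-related, up to 10×ULN with bilirubin below 2×ULN, would stay on treatment even with a matching row. A reader might infer that patients lose a stop rule. They do not: the stop above 10×ULN and the hold for bilirubin above 2×ULN work at every baseline.

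**Sites are not left without instruction.** This also stands. The hepatotoxicity text still requires liver monitoring throughout, immediate tests for suggestive symptoms with review before the next dose, a search for other causes, and imaging. It asks sites to consider autoantibody tests. None of this says whether to hold or continue.

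**The fallback rules do not contradict each other.** Partly right. Body Table 3 concerns cobimetinib and Appendix 9 concerns atezolizumab, so that pair is compatible. Table 4 can be read as a general default for Arms A and B, and its main Grade 3 or 4 instruction is to interrupt. Protocol 5.1.4.3 also sends immune-related events in Arm A to Appendix 9, with an example list that omits hepatic events but is not exclusive. The difference between Table 4's laboratory-only permission and Appendix 9's permanent stop remains, and nothing ranks them.

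**The rash lines can be read in sequence:** restart at Grade 2, then stop if Grade 1 is not reached by week 12. That is possible, and the stop line does bring in the Medical Monitor. But the first line has its own stop clause at the Grade 2 threshold, which would then do no work, and a patient first reaching Grade 2 near week 12 still meets both lines.

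**The percentages are widths of a number line, not patients.** Correct. A reader might take 100% as a share of patients, or think any raised baseline has no row until 10×ULN. Neither is supported: complete absence needs a baseline of at least 2×ULN and a value above 3×ULN, and some uncovered rises are trivial, such as 4.0 to 4.1×ULN.

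**Conclusion.** Both defects are in the current text and follow from its wording.

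The rash conflict is confined to one cell and one situation: a Grade 3 rash that stands at Grade 2 at week 12. Either threshold could be the intended one.

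The liver gap, given bilirubin below 2×ULN, is complete for eligible baselines of 2–5×ULN over values above baseline from over 3 to 10×ULN. It is partial between 1 and 2×ULN. Its clinical weight falls as baseline rises, since the largest uncovered rise shrinks from 5-fold at 2×ULN to 2-fold at 5×ULN. The loss is the weekly tests, the referral, biopsy and steroid prompts, and the atezolizumab hold for suspected immune-related events.

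The documents do not state how many patients enter with such baselines, so no patient count is possible. Alpha, power, events and sample size are unaffected, and a reader should not infer any threat to the overall survival comparison. This is a safety-wording correction that should be made.

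**What to change.** 1. **Rash cell.** Use one threshold in both atezolizumab lines. Grade 1 or better matches Appendix 9, Table 9. The sponsor should confirm it clinically, because Table 3 itself continues treatment for a new Grade 2 rash.
2. **Liver rows 2 and 3.** Restate them as above 3 to 5×ULN and above 5 to 10×ULN. With row 1 and the stop row, these cover every value above ULN once, at any baseline, when bilirubin is below 2×ULN. Add an explicit multiple-of-baseline rule for patients who enter above normal. Without it, someone enrolled at over 3 to 5×ULN would sit in row 2 on Day 1.
3. **Governing rule.** Add one sentence naming the rule for Arm A hepatic events, with the sponsor confirming whether Appendix 3, Table 2 or the stricter Appendix 9 rule applies at Grade 3.

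The cost is wording in two tables, one sentence, and a clarification letter to sites after clinical confirmation. It needs no extra patients, procedures or statistical changes.
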